7.2 SURVIVAL ANALYSIS

[figure not shown]
Survival analysis, also called time to event analysis, will be used in the current research to estimate the time to treatment discontinuation, time to progression, and PFS in 1L. This method of analysis is employed when non-informative right-censoring occurs as is the case for this study since not all patients will have discontinued treatment, progressed or died by the end of the study period. The Kaplan-Meier method (product limit estimator) will be used to generate median estimates of time to progression and PFS if median time is reached within the population. Survival curves will also be generated. In addition to calculating the median survival estimate, the life-table method will be used to estimate these time to event outcomes at successive 3 month intervals through 24 months post initiation of 1L.

The following lists the measurements to be conducted using survival analysis techniques:

1. Median time to treatment discontinuation
 - a. Proportion of patients (survival estimate and 95% confidence interval) who are still receiving 1L treatment at 3, 6, 12, 18, and 24 months post 1L initiation
 - b. Event = any treatment discontinuation for any reason, censor = patients who are still on 1L therapy at data cut-off
2. Median time to progression
 - a. Proportion of patients (survival estimate and 95% confidence interval) who are progression free at 3, 6, 12, 18, and 24 months
 - b. Event = any treatment discontinuation for disease progression, censor = patients who are still on 1L therapy or who discontinued therapy for any reason other than disease progression at data cut-off
3. Median progression-free survival
 - a. Proportion of patients (survival estimate and 95% confidence interval) who are progression free and alive at 3, 6, 12, 18, and 24 months

- b. Event = any treatment discontinuation for disease progression or death, censor = patients who are still on 1L therapy or who discontinued therapy for any reason other than disease progression or death at data cut-off
- 4. Proportion of patients alive at 3, 6, 12, 18, and 24 months following 1L initiation
 - a. Event = death, censor = date of last follow-up among patients who are not deceased

CC
I

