8.6. Data Management

All study data will be entered into the eCRF. The eCRF is designed to allow providers to efficiently move through the patient chart or electronic medical record (EMR) based on the journey of the patient through the course of their disease. The eCRF conforms to the rules and regulations of the Health Insurance Portability and Accountability Act (HIPAA) of 1996 governing the abstraction and storage of protected health information (PHI). No protected health information will be collected in the course of the chart review or stored in the eCRF.

Physicians will be compensated through an honoraria payment for each completed and validated eCRF. The eCRF is anticipated to take up to 45 minutes per patient to complete, and the rate of payment to providers for participation in this study is \$300/completed and validated eCRF. Participating physicians will be asked to complete the chart review individually, meaning that site research staff or supportive staff will not complete any data abstraction.

Cardinal Health will be responsible for the programming, testing, and hosting of data from submitted eCRFs. Providers will access the eCRF through a secure web-based portal, including during the field testing procedures, with all data stored on encrypted, password protected and HIPAA compliant servers housed within the Cardinal Health electronic data storage infrastructure. Cardinal Health will perform extensive testing of the eCRF to ensure functionality across web-based user environments, looping logic to ensure proper alignment of data-related fields (required responses to certain fields prior to entering data into subsequent field), and other programmatic checks to ensure the reduction of the input of erroneous data (such as specifying maximums for year of birth or initiation of first-line treatment within the dates of the enrollment period). In addition, the eCRF will be field-tested among 4 providers to ensure its functionality, the correct interpretation of the questions in relation to the data points of interest, and the length of time required for

completion for a single patient. The pre-test results will be reviewed by Pfizer with Cardinal Health staff; however, Pfizer will not have access to the individual data collected. Any changes made to the eCRF document as a result of the pre-test will require the resubmission of the eCRF and study protocol to the IRB.

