8.9. Limitations of the Research Methods

The key limitation of this research and research of this nature involving retrospective medical chart review abstraction by a patient's treating providers is the reliance on the provider to accurately complete the eCRF. In order to ensure clarity and consistency in reporting, the eCRF will be internally and externally pre-tested. In addition, clinical data quality review will be conducted for each eCRF and invalid or outlier data will be flagged for further review with the treating clinician by Cardinal Health clinical research staff.

Several other limitations impact the external generalizability the results of this retrospective cohort study. Given that providers abstract data on selected patients there is an opportunity for the following to occur: (1) provider selection bias; (2) patient selection bias; (3) and information bias, related to the availability and quality of data contained within the patient charts.

In terms of the representativeness of the provider cohort by imposing a maximum number of eCRFs which can be completed this bias is reduced. With a maximum of 20 eCRFs, the minimum number of providers participating is 30. While the number of providers to be recruited is not specified, not all providers will submit the maximum number of patients. In past research of this nature, the median number of eCRFs submitted per provider is 10. Based on this assessment, the expected number of providers participating is 60. Providers invited to participate but not participating in the research will not be described.

In this study, the magnitude of a patient selection bias will be assessed by quantifying the number of potentially eligible patients and the number of patients submitted for inclusion by the provider. To address this potential bias, providers may only contribute a maximum of 20 patient eCRFs, of which, no more than 10 eCRFs may be submitted for any single treatment group. Differences between providers submitting fewer than 5 versus more than 5 eCRFs may be explored to assess systematic differences and address the potential selection bias.

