2.1 STUDY POPULATION

CCI

[REDACTED]

- 1) Patients treated with palbociclib+LET as initial endocrine therapy for MBC per the palbociclib U.S. FDA approval label;

CCI

[REDACTED]

The target sample size for each of the three cohorts is 200 patients. Table 1 illustrates the selection criteria for each of the cohorts. Patients must meet all of the following inclusion criteria to be eligible for inclusion in the study. No exclusion criteria will be imposed for the selection of patients.

Table 1. Cohort Selection Criteria.

Palbociclib+LET	CCI
Diagnosed with locoregional recurrent or metastatic female breast cancer	
Pathologically confirmed HR-positive/HER2-negative tumor	
Received treatment with palbociclib in combination with LET as initial endocrine-based therapy for advanced/metastatic breast cancer 
 - Initiated treatment with palbociclib at least 3 months following the provider's first use of palbociclib after 03 Feb 2015 - At least 1 month of follow-up data after initiation of palbociclib 	
Postmenopausal (or receiving surgical or medical treatment to induce menopause) at the time of initiation of 1L treatment for locoregional recurrent or BMC	
≥18 year old at initiation of endocrine therapy	

Patient eligibility will be confirmed by the treating physician. Providers may complete a maximum of 20 eCRFs. Providers will be asked to randomly select patients from the pool of eligible patients and verify that they have performed random patient selection.

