5.4 DISEASE RESPONSE TO THERAPY

For this analysis, beyond the variables considered in section 5, non time-to-event clinical outcomes of interest will include the objective response rate (ORR), which is defined as the sum of CR+PR and clinical benefit rate (CBR), which is defined as the sum of CR+PR+SD (lasting >24 weeks). Both the ORR and CBR will be evaluated according to the provider assessed response to therapy.

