5.5 PROGRESSION RATE AND PROGRESSION-FREE SURVIVAL

Disease progression is taken to have occurred when a pathology report or radiological scan note indicates disease progression and/or there is a physician progress note consistent with that determination. Providers will be informed of these criteria and indicate the date of disease progression during initial endocrine therapy for MBC following that guidance.

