7 STATISTICAL METHODOLOGY AND STATISTICAL ANALYSES

7.1 DESCRIPTIVE ANALYSIS

All categorical or numeric non time-to-event variables collected from the chart data abstraction or calculated from said data will be analyzed using descriptive statistical techniques. For demographic continuous variables, the mean, standard deviation, median, and minimum/maximum will be calculated as appropriate. For categorical variables, frequencies and percentages will be provided. The number of missing or unknown observations will be described for both categorical and numeric variables. The 95% confidence intervals will be provided as a measure of estimated precision when appropriate. The following characteristics will be described using in each cohort using the statistical techniques previously described: demographics, receipt of and treatment received for neo/adjuvant treatment, clinical characteristics at diagnosis (e.g., stage, nodal status, menopause status), and clinical characteristics at diagnosis of locoregional recurrent or metastatic/initiation of 1L treatment (e.g., comorbidities, ECOG-PS, menopause status, receipt of CBC/cardiac tests in 30 days prior to initiation of 1L). Other descriptive analyses will include assessing the time from diagnosis to the initial initiation of 1L, duration of adjuvant treatment, and duration of follow-up from initiation of 1L treatment.

In addition, during 1L treatment, the following will be described: dose reductions, dose increases, treatment interruptions, and number of palbociclib cycles completed. The following details the assessment of these outcomes. Response levels are those specified in the case report form for the study.

1. Frequency of initiation of 1L palbociclib at 125mg, 100mg, and 75mg
CCI
[REDACTED]
2. Frequency/proportion of patients with any dose reductions and any dose increase
3. Frequency of reported rationale(s) for dose reduction (toxicity, other) and dose increases (no response, suboptimal response, loss of response, disease progression, other)
4. Mean months from initiation of 1L treatment to first dose reduction, first dose increase
5. Frequency of any treatment interruption; mean number of treatment interruptions during 1L treatment
6. Frequency of reported rationale(s) for first treatment interruption (toxicity, no response, loss of response, disease progression, prepare for alternative treatment strategy, patient choice, other)
7. Mean time to first treatment interruption

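### The 95% confidence intervals in SAP 7.1 and 7.2 take no account of clustering by provider, although one physician selects, assesses and abstracts up to 10 palbociclib+LET patients

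*SAP*

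**What the plan says.** SAP 7.2 uses Kaplan-Meier and life-table estimates. Items 1a, 2a and 3a attach a 95% interval to the landmark estimates for time to discontinuation, time to progression and PFS; for PFS the item reads "Proportion of patients (survival estimate and 95% confidence interval) who are progression free and alive at 3, 6, 12, 18, and 24 months". Item 4 (proportion alive) promises no interval. For the other summaries SAP 7.1 states: "The 95% confidence intervals will be provided as a measure of estimated precision when appropriate". Neither section names a variance method or mentions the provider.

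The provider's role is set out elsewhere:

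- Selection (SAP 2.1): "Providers will be asked to randomly select patients from the pool of eligible patients and verify that they have performed random patient selection".
- Response (SAP 5.4): "Both the ORR and CBR will be evaluated according to the provider assessed response to therapy".
- Progression (SAP 5.5): "Providers will be informed of these criteria and indicate the date of disease progression during initial endocrine therapy for MBC following that guidance".
- Abstraction (Protocol 8.6): "Participating physicians will be asked to complete the chart review individually", without help from site staff.
- Number of patients (Protocol 8.9): at most 20 eCRFs per provider, and "no more than 10 eCRFs may be submitted for any single treatment group".

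The only clustered variance in readable text is in SAP 7.4, for matched sets in the Cox model. Text after item 4 of SAP 7.2, all of 7.3, the start of 7.4 and a block after 7.5 are blacked out. This point therefore concerns the readable text of 7.1 and 7.2 only.

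**The concern.** Patients from the same physician share a selection process, a way of rating response, a way of recording progression and an abstractor. If outcomes correlate within provider for any of these reasons, 200 patients carry less information than 200 independent ones. The usual intervals do not reflect this and are then too narrow.

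The study is descriptive and has no sample-size calculation (Protocol, Abstract), so the intervals are its only statement of precision. Better precision on response and PFS is also part of its stated rationale (Protocol 6). The plan already treats the provider as a source of variation. Protocol 8.9 caps submissions and considers comparing low and high submitters, and SAP 2.2 can drop every record from a provider whose data cannot be validated. None of this enters the standard errors.

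**Working it through.** **Number of clusters.** SAP 2.1 states: "The target sample size for each of the three cohorts is 200 patients". That gives 3 × 200 = 600 patients. Protocol 8.9 states a minimum of 30 and an expected 60 providers. Both reproduce: 600/20 = 30, and 600/10 = 60, where 10 is the median number of eCRFs per provider in past work. For the palbociclib+LET cohort the mean cluster size m is:

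- 60 providers: 200/60 = 3.33
- 30 providers: 200/30 = 6.67, if the cohorts split evenly
- every provider at the limit of 10: 200/10 = 20 providers, m = 10

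**Assumption.** The documents give no ICC. Values of 0.02, 0.05 and 0.10 are assumed throughout.

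**A proportion, such as ORR.** The feasibility query (Protocol 8.5) gives (126 + 340)/804 = 58.0%. Under independence the half-width is 1.96 × √(0.580 × 0.420/200) = 6.84 points. With clustering:

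- design effect DEFF = 1 + (m − 1) × ICC
- half-width needed = 6.84 × √DEFF
- true coverage of the unadjusted interval = P(|Z| < 1.96/√DEFF)

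| Providers | DEFF at ICC 0.02 / 0.05 / 0.10 | Half-width needed (points) | Coverage of unadjusted 95% CI |
|---|---|---|---|
| 60 | 1.047 / 1.117 / 1.233 | 7.00 / 7.23 / 7.60 | 94.5 / 93.6 / 92.2% |
| 30 | 1.113 / 1.283 / 1.567 | 7.22 / 7.75 / 8.56 | 93.7 / 91.6 / 88.3% |
| 20 | 1.18 / 1.45 / 1.90 | 7.43 / 8.24 / 9.43 | 92.9 / 89.6 / 84.5% |

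Example, 30 providers and ICC 0.10: DEFF = 1 + 5.67 × 0.10 = 1.567; 6.84 × √1.567 = 8.56.

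**The 24-month PFS landmark.** Censoring makes the simple formula approximate, so this was simulated with 10,000 runs per scenario.

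- N = 200 in near-equal provider clusters.
- True 24-month PFS is 64.3%, the real-world figure in Protocol 6.
- Each provider's 24-month PFS is drawn from a Beta distribution with that mean and the given ICC; times within a provider are exponential.
- Follow-up is assumed uniform over 12 to 42 months, so 29% of patients are censored before 24 months.

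The interval checked is the standard Kaplan-Meier interval (Greenwood variance, log-log scale). Its mean half-width is 7.1 points.

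| Providers | Coverage at ICC 0 | Coverage at ICC 0.02 / 0.05 / 0.10 | Half-width needed (points) |
|---|---|---|---|
| 60 | 95.1% | 94.5 / 93.8 / 92.4% | 7.3 / 7.5 / 7.8 |
| 30 | 95.1% | 93.8 / 92.1 / 89.3% | 7.5 / 8.0 / 8.7 |
| 20 | 94.8% | 93.5 / 90.9 / 85.9% | 7.6 / 8.4 / 9.5 |

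The Monte Carlo standard error is about 0.2 to 0.35 points. With 0% to 42% censored before 24 months, coverage at ICC 0.10 is 92.4–92.9% (60 providers), 89.3–89.9% (30) and 85.1–88.0% (20).

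**Does a clustered interval work?** In the same simulation (29% censored), a provider-clustered variance multiplied by K/(K − 1), with a t quantile on K − 1 degrees of freedom (K = number of providers), covered 94.5–94.7% at 60 providers, 94.6–94.7% at 30 and 94.6–94.9% at 20. Without the small-cluster correction it covered 93.8–94.0%, 93.2–93.3% and 92.6–93.1%.

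**The case against.** The strongest reply concerns size. At the expected 60 providers and an ICC of 0.02 to 0.05, coverage is 94.5% to 93.8%, and the half-width should be 7.3 to 7.5 points instead of 7.1. Few readers of a descriptive estimate would notice. Exactly 30 providers requires every one to submit 20 eCRFs, which Protocol 8.9 itself does not expect, and 20 providers requires all to reach the limit of 10. An ICC of 0.10 implies a between-provider standard deviation in 24-month PFS of √(0.10 × 0.643 × 0.357) = 15 points, which no document supports. Random selection, the outlier review (Protocol 8.8) and the screening of deviating response patterns (SAP 2.2) may lower the correlation. The abstractor may also be copying dates that colleagues in the practice recorded. An interval for ORR is not firmly promised. The SAP names no variance method, and a general statement could sit in the redacted text.

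Much of this stands as a limit on size. It does not show that patients of one provider are independent, and the estimators the SAP names have standard intervals that assume they are. One omission works the other way: the tables use near-equal clusters. If, for illustration, 10 of 60 providers submit 10 patients each and the other 50 submit 2 each, simulated coverage (4,000 runs) is 93.8, 92.4 and 90.0% at the three ICCs. In addition, the limit of 10 per treatment group appears only in Protocol 8.9; Protocol 8.1 and 8.2 and SAP 2.1 state only the maximum of 20.

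**Conclusion.** The concern holds for the readable text of SAP 7.1 and 7.2. The planned intervals are too narrow if outcomes correlate at all within provider. The effect is modest at 60 similar-sized providers, grows as the number falls towards 30 or contributions become uneven, and is large only in the limiting case of 20 providers with 10 patients each. These sizes rest on an assumed ICC of 0.02 to 0.10 and, for the landmark, on the assumed follow-up pattern. Only interval width and coverage are affected. The change is worth making because the intervals are the study's only statement of precision and the remedy is cheap.

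**What to change.** State in SAP 7.1 and 7.2 that 95% intervals for overall proportions and landmark estimates use the provider as the cluster. Use either a cluster-robust variance with a named small-cluster correction (for example t on K − 1 degrees of freedom) or resampling of whole providers. Report the number of providers and the distribution of patients per provider beside the results; Protocol 8.9 already plans to count the patients each provider submits.

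The cost is SAP wording and some non-default programming for the Kaplan-Meier and life-table intervals. No new data are needed, because the submitting provider of each eCRF is already known (Protocol 8.8, SAP 2.2). Over the three ICCs the mean landmark half-width would rise from 7.1 points to 7.4–7.9 at 60 providers, 7.7–9.0 at 30 and 8.0–10.0 at 20. If there is in fact no within-provider correlation, the increase is only about 0.1, 0.2 or 0.4 points respectively. Wider intervals do not address the selection bias that Protocol 8.9 acknowledges.

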8.3. Variables

For purposes of this study, a regimen will be defined as one or more anti-cancer agents given in combination, over a period of time. Providers will be informed as to the definition of a regimen *but will make the determination themselves as to what constituted a line of therapy in the advanced/metastatic setting*. However, re-assignment of the lines of therapy in the metastatic setting may occur during data analysis based on the dates regimens were initiated and discontinued and the rationale for that discontinuation. For example a patient treated with palbociclib+LET who discontinued palbociclib but continued with LET may be indicated as a single line by the provider but the use of LET monotherapy may be recoded as a subsequent line of therapy during the analysis phase. All dates of initiation and discontinuation of individual agents when received in combination will be abstracted by the patient's treating physician.

Additionally, disease progression is taken to have occurred when a pathology report or radiological scan note indicates disease progression and/or there is a physician progress note consistent with that determination. Providers will be informed of these criteria and indicate the date of disease progression as recorded in the patient charts during initial endocrine therapy for MBC following that guidance.

The table below describes data elements to be abstracted by the provider (“Abstracted Data Points”) and independent/exposure variables calculated from the abstracted data (“Calculated Variables”).

Variable	Operational definition
Patient demographics	Abstracted Data Points: Year of birth, payer, state of residence, ethnicity, weight, height, ER status, PR status, HER2 status, family history of breast cancer. Calculated Variables: age at advanced/metastatic diagnosis, age at initiation of endocrine-based therapy, body mass index.
Clinical characteristics	Abstracted Data Elements: date of initial breast cancer diagnosis, date of diagnosis of advanced/metastatic disease, AJCC stage, node status, menopause status, ECOG-PS (@ treatment for advanced/metastatic disease), sites of metastatic disease (@ initiation of treatment for advanced/metastatic disease), comorbidities (@ initiation of treatment for advanced/metastatic disease). Calculated Variables: time to advanced/metastatic disease, Charlson comorbidity index.

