- d. Treatment patterns includes the distribution of regimens administered, by line, from MBC diagnosis through the end of the medical record
- e. Treatment patterns also includes the sequence of treatments across lines, from MBC diagnosis through the end of the medical record

4) Describe the rate of objective disease response during initial endocrine-based therapy

- a. Tumor response will be classified per provider report for each regimen received during MBC treatment
- b. Tumor response will be classified under a primary response classification as complete response (CR), partial response (PR), stable disease (SD), progressive

disease (PD), and not evaluable (NE), and unknown which comprises any other status

- c. Tumor response will be classified under a secondary response classification as matching the primary classification, but for patients with NE, responses classifiable as “Other Favorable” or “Other Unfavorable”

5) Describe PFS from the initiation of initial endocrine-based therapy

- a. Proportion of patients who are persistent to initial endocrine-based therapy for MBC at 3, 6, 12, 18, and 24 months, with persistence defined as the duration of initial regimen until one of the following events occurs: a regimen change or switch, treatment discontinuation, disease progression, or death.
- b. Landmark PFS at 3, 6, 12, 18, and 24 months
- c. Proportion alive at 3, 6, 12, 18 and 24 months

CCI

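### SAP 7.2 counts progression only as a reason for stopping first-line treatment, so items 2b and 3b do not yield the progression-free proportions promised in 2a and 3a

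*SAP*

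**What the plan says.** **Event and censoring rules (SAP 7.2).**
- Item 2b, time to progression: "Event = any treatment discontinuation for disease progression, censor = patients who are still on 1L therapy", together with those who stopped for any reason other than progression.
- Item 3b, PFS: "Event = any treatment discontinuation for disease progression or death, censor = patients who are still on 1L therapy or who discontinued therapy" for a reason other than progression or death.
- Both items end with a reference to data cut-off. Neither says on what date an event is counted.
- Item 4a, survival, does name a date: "Event = death, censor = date of last follow-up among patients who are not deceased".

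**What those rules are meant to deliver.** Item 2a promises the proportion of patients "who are progression free at 3, 6, 12, 18, and 24 months". Item 3a promises the proportion "who are progression free and alive at 3, 6, 12, 18, and 24 months".

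**What progression is.** SAP 5.5 reads "Disease progression is taken to have occurred when a pathology report or radiological scan note indicates disease progression", with a consistent physician progress note also accepted. Protocol 8.3 uses the same definition and asks providers to "indicate the date of disease progression as recorded in the patient charts during initial endocrine therapy for MBC". SAP Table 2 lists the progression date among the clinical outcomes and the 1L discontinuation date in a separate row.

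**Death.** SAP 7.1 item 10 includes death among the coded reasons for discontinuing 1L. The role column of SAP Table 2, in the row on status at last follow-up, says that death enters the PFS calculation.

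**The concern.** Two different events are in play. SAP 5.5 and protocol 8.3 describe something seen in the chart, with its own date. Items 2b and 3b describe a treatment decision and the reason recorded for it. They coincide only if every documented progression leads to an immediate stop that is coded as progression.

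The plan leaves room for the two to differ. SAP 2.4 objective 5a ends persistence at the first of "a regimen change or switch, treatment discontinuation, disease progression, or death", so stopping and progressing are separate items. SAP 7.1 items 3 and 6 offer progression as a reason for a dose increase or an interruption, and neither of these is a discontinuation.

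Landmark PFS is a stated objective (SAP 2.4, objective 5b; protocol 7.1, objective 4b). The SAP introduction sets it beside an earlier chart review's 24-month progression-free rate of 64.3% and the trial median of 24.8 months. An estimate that leaves out some documented progressions, or dates them late, is not the quantity its label claims. The Cox model for risk of progression in SAP 7.4 has no event definition of its own in the visible text and would presumably inherit the same rule.

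**Working it through.** The plan derives no figure from this definition, so there is none to reproduce. The check has two parts.

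**1. Classifying patients under each text**

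| Patient | Documented progression (SAP 5.5, protocol 8.3) | SAP 7.2 items 2b/3b |
|---|---|---|
| Progression documented, 1L stopped at once, reason progression | Progressed, on the abstracted date | Event |
| Progression documented, 1L continues to the end of follow-up | Progressed | Censored: still on 1L |
| Progression documented, 1L stopped later for progression | Progressed, on the abstracted date | Event, time not stated; later if dated at the stop |
| Progression documented, stop coded to another reason | Progressed | Censored |
| Stopped without progression, died later | Not addressed in 5.5 | Unclear in 3b |

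The second and fourth rows are mismatches. The third is a mismatch if the stop date is used. The last turns on grammar: 3b can mean discontinuation for either progression or death, or discontinuation for progression, or else death. SAP 7.1 item 10 favours the first reading and the Table 2 role entry favours the second.

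**2. Illustration of size**

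Input from the documents: median 24.8 months (protocol section 6). Everything else is assumed:
- exponential progression;
- a share p of progressors stays on 1L for an exponential time of mean D months: (p, D) = (10%, 3), (20%, 6), (30%, 12);
- follow-up unrelated to progression.

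Documented date: λ = ln 2 / 24.8 = 0.02795 per month, so S(24) = exp(−24λ) = 51.1%.

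(a) *Event dated at the stop.* With d = 1/D, the proportion of delayed patients without a stop for progression by 24 months is G = [d·exp(−24λ) − λ·exp(−24d)] / (d − λ), which is 55.8%, 61.1% and 70.1%. The mixture is (1 − p)·51.1% + p·G:
- 0.9 × 51.13 + 0.1 × 55.81 = 51.6%
- 0.8 × 51.13 + 0.2 × 61.06 = 53.1%
- 0.7 × 51.13 + 0.3 × 70.10 = 56.8%

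The medians become 25.1, 26.2 and 28.9 months.

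(b) *Event on the documented date, but progressors still on 1L censored at last follow-up.* Simulated Kaplan-Meier at 24 months:
- follow-up uniform over 1 to 46 months: about 51.5%, 52.6% and 55.5%, with about 0.9, 3.5 and 9.4 progressions uncounted per 200 patients;
- follow-up uniform over 24 to 46 months: about 51.3%, 51.7% and 53.7%.

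(c) *Stop coded to another reason.* If 10% of progressions, at random, carry another stop reason and are censored at an immediate stop, the hazard falls to 0.9λ and S(24) = exp(−0.9 × 24λ) = 54.7%.

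**Scale and direction.** The simulated standard error at n = 200 with 1 to 46 months of follow-up is 4.2 points. The shifts in (a) of 0.5, 2.0 and 5.7 points are thus about 0.1, 0.5 and 1.4 standard errors. The upward direction holds on average, not in every sample: in simulated samples of 200, the stop-dated estimate fell below the documented-date estimate in about 39%, 6% and 0.2%.

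**The case against.** The best defence is that an on-treatment measure was intended. SAP 7.2 announces PFS in 1L, and the progression date is sought only during initial endocrine therapy. SAP 5.5 sets no time-to-event rule, so 7.2 can borrow its meaning of progression and add its own event. That answers anyone who infers that the two sections cannot both be programmed: they can. It does not rescue 2b and 3b, because an on-treatment analysis should still count progression documented on treatment, and 2a and 3a promise exactly that.

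Three other objections stand in part.
- **Deaths.** A reader might infer that 3b excludes deaths after a non-progression stop. The documents do not settle this, because the Table 2 role entry points the other way. The same row refers to a section 5.1.5 that is not in the available text, and nothing can be drawn from that.
- **Censoring time.** A reader might infer that 2b and 3b contain no timing at all. They do refer to data cut-off. The fault is that this may describe a patient's status or set the censoring time.
- **Frequency.** The options in 7.1 items 3 and 6 show what the form allows, not how often it happens. Objective 5a makes progression itself end persistence, so it separates the two events without showing that treatment continues after progression.

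Redacted text follows item 4, but it cannot alter the visible wording of 2b and 3b.

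**Conclusion.** The point stands as a mismatch between the event rule and the quantity promised. Documented progression on continuing 1L, or followed by a stop coded otherwise, is not an event under 2b or 3b. Event time is unstated, censoring time is ambiguous, and so is the place of later deaths in PFS. It should be fixed before analysis.

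A reader might go further and infer that reported PFS will be materially inflated. The documents do not support that. They give no rate of treatment past progression, no delay and no follow-up distribution. In the illustration the 24-month figure rises by about 0.5 to 5.7 points with stop-dated events. With progressors still on 1L censored, the rise is about 0.2 to 2.6 points under the longer follow-up and 0.4 to 4.4 under the wider range. All of this rests on assumed inputs and on censoring unrelated to progression. If progression almost always brings an immediate stop with that reason, the effect is close to nil. The case for change is the mismatch and the low cost of removing it, not a demonstrated bias.

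**What to change.** - **Item 2b:** event = first progression documented as in SAP 5.5, on its abstracted date, whether or not 1L stops.
- **Item 3b:** event = the earlier of that date and death. State whether deaths after the end of 1L count.
- **Censoring:** name a date for each group. For example, use last follow-up for patients still on 1L without progression and, in an on-treatment analysis, the 1L discontinuation date for those who stopped without progression.
- **Label:** call the estimate on-treatment PFS if progression after 1L is not captured.
- **SAP 7.4:** use the same event in the Cox model for risk of progression.
- The present rule could be kept as a separately named time to discontinuation due to progression.

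The cost is the wording of 2b and 3b, the affected table shells and the Cox event definition. Progression, 1L discontinuation, last follow-up and death dates are already listed for abstraction in SAP Table 2 and protocol 8.3, so no eCRF field is added. Reported PFS may be slightly less favourable.
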